"Normal" aging is associated with declines in learning and memory, such as losing or misplacing personal items, a complaint often reported by older adults. These complaints parallel neurological changes that occur in late-life; for example, the specific complaint of misplacing household items, known as a failure in object location association (OLA) memory, relies on several brain regions, including frontal, parietal, and medial temporal regions, that work together to bind object and location information into long-term memory (Postma et al., 2008; Gillis et al., 2016; [name] et al., 2016). We previously demonstrated overlap in the same frontoparietal regions involved in OLA memory and working memory (Gillis et al., 2016). The current pilot study investigates whether a single session of High Definition transcranial direct current stimulation (HD-tDCS) affected performance on one, or both, of these cognitive abilities.

HD-tDCS modulates neuronal excitability and is generally considered safe and well tolerated. This method offers improved focality relative to the standard pad-based approach to tDCS (Edwards et al., 2013; Datta et al., 2009). Our recent safety review revealed that about 96% of tDCS sessions used some variant of 1 or 2 milliamp (mA; Bikson et al., 2016). The arbitrary cap at 2 mA has no theoretical or empirical justification, since available evidence suggests a current intensity of 167 mA (or greater) would be needed to induce tissue damage. Thus, the current pilot study will use a current intensity of 3 mA in order to evaluate the effects on cognition while also evaluating tolerability and safety of this under investigated dosage.

tDCS Safety Considerations. According to a review encompassing tDCS studies conducted through 2016, tDCS is a safe intervention with no reported cases of severe or unexpected adverse events, tissue damage, or irreversible brain injury in over 33,200 conventional sessions (duration \leq 40 minutes, current \leq 4 mA; Bikson et al., 2016). Furthermore, no serious adverse events have been reported in 'vulnerable' populations, including children, older adults, and individuals with epilepsy, stroke history, or implanted devices (Bikson et al., 2016). There is little evidence to indicate that higher dosage of intensity or duration is unsafe (Bikson et al., 2016).

We conducted an *a priori* power analysis for two-tailed mean comparisons between Active and Sham participants on OLA and working memory measures (see Measures section below), based on the estimated effect size from a meta-analysis of single-session anodal tDCS to the dorsolateral prefrontal cortex (DLPFC) of healthy adults (Hedges $g = 0.254$ for sham vs. tDCS accuracy effects; Brunoni and Vanderhasselt., 2014). At a power level of 0.80, the required sample size to achieve an effect size of 0.25 was 10 participants per group; therefore, we will recruit at least 30 total participants (15 per group) to ensure adequate power.

Participants

Participants will include 40 right-handed, cognitively intact, community-dwelling older adults, age 50+. Participants will be recruited from the University of Michigan Neuropsychology Clinic, the Michigan Alzheimer's Disease Center, the University of Michigan Health Research Registry and the surrounding community. All study-related activities will occur at the University of Michigan.

Inclusion Criteria

Those participants who have recently undergone testing demonstrating no significant cognitive impairments (Mini-Mental Status Exam [MMSE] score > 23 within last six months) will be accepted into the study. For potential participants without recent cognitive testing, we will perform the MMSE following informed consent in order to establish cognitive status. All participants are also screened to ensure that they meet criteria to participate. All participants received \$10 for participation in the study.

Exclusion Criteria

General exclusion criteria include a history of traumatic brain injury (by patient report or available medical record), diagnosed neurologic disease (including Parkinson's disease, dementia, epilepsy, multiple sclerosis, or tumor), severe mental illness (e.g., bipolar disorder, schizophrenia, other psychotic disorder), substance use disorders, and cognition-impacting medications (anticonvulsants, antipsychotics, anxiolytics). Individuals with skull plates or other implants impacting tDCS current flow will not be enrolled in the study. Individuals with significant visual impairments that limit ability to see stimuli, or motor impairments that may interfere with ability to participate in the touchscreen task will also be excluded. To ensure appropriate electrode-scalp contact required for stimulation to be safely and effectively administered, participants with scalp dermatitis or limiting hair styles will be excluded. To clarify future interpretation of results, individuals with significant alcohol or recreational drug use or poor sleep within the 24-hours prior to the stimulation session will be excluded from the study. Individuals currently participating in other neuromodulation studies are not eligible to participate.

Recruitment Strategy

HD-tDCS. Participants will undergo a single session of active or sham 4x1 high-definition transcranial direct current stimulation using a Soterix 1x1 TES device and attached 4x1 Multichannel Stimulation Adaptor. HD-AtDCS uses small gel-based electrodes (as opposed to conventional tDCS, which uses large, fluid-soaked sponge electrodes) to deliver a more localized current to specific brain regions. The montage is designated 4x1, as it utilizes a central electrode that defines the polarity of the stimulation (anodal in the current study), surrounded by four return electrodes that constrict the area of excitability. In order to target OLA memory, researchers will employ stimulation under the anode placed over the left lateral prefrontal cortex at the inferior frontal gyrus (F5 in the 10/20 International system). Participants undergoing active stimulation will receive 20 minutes of stimulation at 3 mA. Conversely, participants undergoing sham stimulation will receive a 10-second ramp-up, 30-second stimulation at 3 mA, and 10-second ramp-down, followed by approximately 19 minutes without stimulation, and a second ramp-up/ramp-down period. These short periods of stimulation are completed for effective blinding of participants. Step-by-step procedures for HD-tDCS set-up and stimulation are detailed below under 'Participant Timeline of Procedures'.

Primary Outcomes

Object Location Touchscreen Task (OLTT; [name] et al., 2011; England et al., 2015).

Participants will undergo the OLTT, an ecologically relevant measure of object location association

memory. The OLTT requires participants to learn and recall the location of 15 object-location associations. Memory is evaluated using a touchscreen monitor, which allows for the continuous measurement of memory accuracy (i.e., distance from targeted location).

N-Back Working Memory Tasks. The n-back is a well validated measure of working memory. Participants will complete the same n-back paradigm, which includes 0-back and 2-back conditions, as in our earlier study (Gillis et al., 2016). Additionally, a semantic 2-back condition will be used that requires participants to state whether a given object is of the same semantic category as the one presented two items ago.

Secondary Outcomes

Tolerability

Immediately following stimulation, participants will complete an adapted form of the side-effect questionnaire developed by Brunoni and colleagues (2011; see Figure 1). We will delay examining the skin for redness until after the participant has completed the condition estimate (see below) in order to avoid any potential bias that could impact blinding. For further information on safety monitoring plan, see the 'Methods: Monitoring' section below.

Effectiveness of Blinding

After completing the side-effect questionnaire, participants will be asked to state which stimulation condition they believed they received (referred to as "condition estimate" in this document; i.e., active/"real", sham/"fake", or "I don't know").

Participant Timeline of Procedures

1. Participants will complete an initial telephone screening prior to ensure basic eligibility. Participants who meet inclusion criteria will be scheduled for a two-hour appointment within approximately one week of initial screening (allowing for the participant's schedule).
2. During the study session, participants will first provide informed, written consent. Additional background and screening questions regarding medical history, acute sleep problems or alcohol use, and other eligibility criteria will be recorded. If not completed within the six months prior to the session, an MMSE will be completed. If additional concerns remain regarding participant eligibility, study team members will confer with *BMH*. If a participant is deemed ineligible at this stage, he or she will still receive the financial compensation for participation, but will be dismissed.
3. Eligible and enrolled participants will begin study procedures by completing the OLTT (Version B).
4. During the 15-minute break between encoding and retrieval, two study team members will measure and mark the electrode locations on the participant's head. A mesh cap will be placed over the participant's scalp and plastic electrode holders placed over the marked locations. Hair will be moved out of the way of these electrode holders, exposing as much scalp as possible. Each holder will be filled with conductive gel and checked for air bubbles using a plastic syringe. Each electrode will be lowered into place using the syringe, and electrode holder caps will be secured into place to eliminate movement of the electrodes during stimulation.

Prior to statistical analyses, data screening will be conducted. Initial steps will include a missing data analysis to determine randomness of missing data and range checks to assess for data quality. Of note, due to unforeseen technical issues, 2-Back Working Memory condition data were lost from the first 11 participants at the outset of the study (at random; no participant-related factors predicted this loss); investigators chose to expand the sample size by 15 participants in order to meet a priori sample sizes. Additional screening for univariate and multivariate outliers, skewness and kurtosis will be conducted to inform needs for data transformation and statistical approach.

Statistical Approach: Primary Outcomes

To compare change in performance on the OLTT Version B (pre-stimulation) and C (post-stimulation) in the active and sham groups, repeated measures analysis of variance (ANOVA) will be used. Specific outcome variables of interest will include Free Recall and Cued Recall average accuracy (in cm) and average reaction time (in ms), Recognition accuracy (number correct), and average Recognition time (in ms).

To assess group differences in N-Back performance, multivariate analysis of variance (MANOVA) was employed, comparing active and sham groups on discriminability (d'). More specifically, d' in the 2-back and Semantic-Back conditions was compared to d' in the 0-back condition as a purer measure of working memory, eliminating the influence of basic processing speed.

Statistical Approach: Secondary Outcomes

To evaluate tolerability on the side effects questionnaire, the frequency of each reported side effect will be evaluated as a function of stimulation condition (i.e., active or sham) using Fisher's Exact Tests. Any severe adverse effects will be reported following established IRB protocols (see Methods: Monitoring). To evaluate blinding, chi-squared tests will be conducted to determine group differences in actual condition assignment vs. estimated/perceived condition.

Methods: Monitoring

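### A single MANOVA drops the 11 participants with lost 2-back data from Semantic-Back too; if their Semantic-Back data survived, that contrast's standard error is about 17% larger at N = 40

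*Combined protocol and SAP*

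**What the plan says.** All references are to the combined protocol and SAP.

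- **The loss.** Data Screening states that "2-Back Working Memory condition data were lost from the first 11 participants at the outset of the study". It attributes this to technical problems and adds that "no participant-related factors predicted this loss".
- **The response.** The same paragraph says that "investigators chose to expand the sample size by 15 participants in order to meet a priori sample sizes".
- **Missing-data provision.** The only one is diagnostic: "Initial steps will include a missing data analysis to determine randomness of missing data". No rule says how a participant with incomplete N-back data enters the analysis, and no analysis set is defined.
- **The N-back analysis.** Under Statistical Approach: Primary Outcomes, "multivariate analysis of variance (MANOVA) was employed, comparing active and sham groups on discriminability". More specifically, d-prime "in the 2-back and Semantic-Back conditions was compared to" d-prime in the 0-back condition. Both working-memory measures therefore sit in one multivariate test.
- **The tasks.** Under N-Back Working Memory Tasks, participants complete "the same n-back paradigm, which includes 0-back and 2-back conditions". The next sentence adds that "a semantic 2-back condition will be used".
- **Status and counts.** N-back performance is one of the two primary outcomes in the summary table on the first page. Objective 1 gives weight to effect sizes because the study is preliminary. The Power Analysis section sets a minimum of 30 participants (15 per group). The summary table and the Participants section both give 40.

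**The concern.** A MANOVA compares vectors of outcomes. A participant with no 2-back value has no complete vector, and standard software drops that person from the whole analysis. The loss of one condition thus becomes a loss of both, even where the Semantic-Back and 0-back data were recorded.

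What is at stake is the precision of one of the N-back effect estimates. In a pilot whose power is low under any reading, the useful product is an effect estimate with its interval. Discarding observed primary-outcome data widens that interval. A reader also cannot tell how many people per arm stand behind each N-back result.

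**Working it through.** The plan states no number of participants for the N-back MANOVA or for either contrast, so there is no figure of its own to reproduce first.

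**1. Does the stated method drop the 11 from both measures?** A standard MANOVA routine (statsmodels), given 40 rows with one of two outcomes missing in 11 of them, used 29 rows for both outcomes. The same follows whether the comparison with 0-back is made by difference scores or by entering three conditions, because each needs a complete vector.

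**2. Did Semantic-Back survive for the 11?** Three points favour survival:
- the report of the loss names the 2-back condition only;
- the analysis section names 2-back and Semantic-Back separately;
- the task description presents the semantic task as an addition to a paradigm of 0-back and 2-back.

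One point leaves doubt: the task description also calls the semantic task a 2-back condition. Survival is the natural reading, but it is not stated.

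**3. Inputs.**
- Lost 2-back data: 11 (Data Screening).
- Final N: 40 as stated in the summary table and Participants. Two alternatives are included because the expansion by 15 has no stated base: 30 + 15 = 45 and 40 + 15 = 55.
- Assumptions: near-equal arms, a common SD, the 11 losses spread about evenly over the arms, loss confined to the 2-back, two-sided 5% level.
- Effect for power: g = 0.254 (Power Analysis), applied to the contrast score.

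**4. Standard error of the Semantic-Back group difference.** In SD units of the contrast score, SE = sqrt(1/n1 + 1/n2). The 95% CI half-width is the t quantile on n1 + n2 − 2 degrees of freedom times the SE.

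At N = 40:
- all participants: sqrt(1/20 + 1/20) = 0.316
- 11 dropped, 29 left: sqrt(1/15 + 1/14) = 0.372
- ratio: 1.175

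| Final N | Arms, all | Arms, 11 dropped | SE, all | SE, dropped | Ratio | Half-width, all | Half-width, dropped |
|---|---|---|---|---|---|---|---|
| 40 | 20/20 | 15/14 | 0.316 | 0.372 | 1.175 | 0.640 | 0.762 |
| 45 | 23/22 | 17/17 | 0.298 | 0.343 | 1.150 | 0.601 | 0.699 |
| 55 | 28/27 | 22/22 | 0.270 | 0.302 | 1.118 | 0.541 | 0.608 |

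If Semantic-Back was also lost for the 11, both analyses use the same people and the ratio is 1.

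**5. Power at g = 0.254** (two-sided two-sample t test), all participants against 11 dropped: 12.3% and 10.1% at N = 40; 13.3% and 11.1% at 45; 15.2% and 13.1% at 55.

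**6. Counts.** 30 + 15 = 45 and 40 + 15 = 55, and neither is the stated 40. A final 40 would need a base of 40 − 15 = 25, which appears nowhere. Participants with 2-back data would number 40 − 11 = 29, 45 − 11 = 34 or 55 − 11 = 44, against the planned minimum of 30.

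**The case against.** The best defence is that the loss was disclosed and acted on. The plan gives the number affected, the technical cause, the absence of participant-related predictors, and a remedy: 15 added, which exceeds the 11 lost. This suggests that the investigators were counting participants with 2-back data. Complete cases also have a merit, because the joint test and both effects then rest on the same people. Power is about 10% or 12% at N = 40, so no conclusion is shown to turn on the choice, and the study calls itself a pilot.

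Most of this stands, and it limits the point to precision. It does not remove the point. Adding participants restores the 2-back count, but it does not bring the first 11 back into the Semantic-Back comparison. The joint test can be kept alongside estimates that use the remaining data.

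Three stronger readings are tempting, and the documents do not support them.

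- **That the loss biases the N-back result.** The plan describes a technical failure unrelated to participants, and nothing in the text contradicts that.
- **That the standard error could be 21% larger.** One route needs a final N of 35, that is, the 10 per group from the power calculation plus 15. But the plan recruits at least 30 and states 40 twice, and 35 is nowhere given as a total. The other route needs an 18/11 split of the remaining 29 at N = 40 (sqrt(1/18 + 1/11) = 0.383; ratio 1.210). With 20 per arm and loss unrelated to arm, a split at least that uneven has a probability of about 3%.
- **That the counts contradict each other.** The 30 is a floor and the 40 a target, so the base of the expansion is a missing number and not a proven inconsistency.

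**Conclusion.** The point holds as a conditional loss of precision. The stated MANOVA, run in the standard way, excludes the 11 from Semantic-Back as well as 2-back. If their Semantic-Back and 0-back data exist, the standard error of the Semantic-Back group difference is about 17% larger than it need be at the stated N of 40. It is about 15% larger if the final N is 45 and 12% larger if it is 55. If Semantic-Back was lost too, the cost is zero. The size rests on near-equal arms and on the 11 falling about evenly across them.

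The missing counts are a secondary reporting matter. The change is worth making because it is cheap and N-back is a primary outcome, not because a conclusion is known to depend on it. Confidence is medium, since survival of the Semantic-Back data is inferred.

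**What to change.** Keep the MANOVA and add text along these lines after it:

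> The MANOVA is a complete-case analysis of participants with d-prime in all three conditions ([n] active, [n] sham). In addition, the group differences in 2-back minus 0-back and in Semantic-Back minus 0-back d-prime are each estimated in all participants with data for that contrast, with effect size, 95% CI and n per arm.

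One mixed model using all available conditions would serve equally well. Because the plan describes the MANOVA in the past tense, the addition should be labelled post hoc if its results have already been seen.

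In Data Screening, state:
- whether 0-back or Semantic-Back data were also lost for the first 11;
- the base and the final N behind the expansion by 15;
- the n per arm for each N-back condition, against the planned minimum of 30.

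The cost is a few sentences and one further analysis of existing data, with no new participants. The downside is that the two contrasts rest on partly different participants, so they are not strictly comparable with each other. If Semantic-Back was also lost for the 11, the added contrasts bring no gain in precision and only the reporting clarification remains.

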All consent forms and others requiring authorized signatures were approved by the University of Michigan IRB. A study team member will review the consent form, emphasizing the relevant aspects of the PCN study to be conducted during this sub-study. The team member will pause after each section to solicit and answer questions. Comprehension of the procedures, risks, benefits, and other aspects of the study will be checked using a decision-making tool (a brief measure asking the participant to use his or her own words to review the contents of each section of the consent form before signing).

Confidentiality

Information gathered from individuals contacted for initial screening is entered into a recruitment database file that is stored in the shared drive (accessible only to select, approved lab personnel) and password protected. This centralized file will contain only the necessary information for contacting and determining eligibility and interest in the study, as well as assigned ID numbers for enrolled participants. For information regarding security and confidentiality of data from enrolled participants, see '**Data Management & Entry**'.

Participants are aware prior to enrollment that they will not receive feedback regarding their performance on cognitive screening or outcome measures, nor information about their stimulation condition assignment. As mentioned above, a copy of the consent form is uploaded into the participant's University of Michigan electronic medical record as a 'Research Document' to communicate current research participation to medical providers.

Declaration of Interests

None of the study investigators have any financial or competing interests to declare.

Access to Data

Study data will remain housed within the [name] laboratory at the University of Michigan and will only be available to authorized study team members or members of oversight committees (e.g., IRB).

Ancillary and Post-Trial Care

As noted above, there are procedures in place to alert the principal investigator and take any needed action to deal with serious adverse events or harms that occur during the study session. As stated in the consent form, participants are instructed to seek immediate medical attention for any serious adverse events that arise after the study session, rather than waiting to contact or hear back from study personnel. Participants are instructed that any medical appointments that are attended after the study will be billed through the patient's regular insurance avenues.

As this study is examining a non-clinical sample of healthy older adults, and HD-tDCS is not considered part of the standard of care for older adults, there is no obligation to provide a waitlist control or delayed access to treatment to individuals assigned to the sham condition.

Dissemination Policy

A summary of results from the current study will be uploaded within one year of study completion to clinicaltrials.gov. At this time, there are no plans to grant public access to the participant level dataset or statistical coding used to analyze data. Findings will be communicated in the form of scientific presentations at national meetings and publications in peer-reviewed scientific journals. There are no restrictions on publications. Authorship will be based on study contribution, considering efforts towards study design, data collection and management, statistical analysis and interpretation, and production of presentations and manuscripts.

References

